7.3.3. Population of Interest

The secondary efficacy analyses will be based on the ITT and Efficacy PD population, unless otherwise specified.

7.3.4. Strategy for Intercurrent (Post-Randomization) Events

Any intercurrent events are taken to be irrelevant for secondary endpoints and the secondary endpoints will be summarized based on available and observed data.

Analysis of change from baseline in the respective iron parameter at each assessment visit will follow the strategy below.

Intercurrent events	Strategy
Study withdrawal / Intermittent missing	The following hypothetical scenario is considered to assess what would have happened if the event did not occur. Analysis using MMRM assume missing at random mechanism, that is the observations of missing depend on just observed values, not on unobserved values.

7.3.5. Statistical Analyses / Methods

Details of the planned displays are provided in [Appendix 10](#): List of Data Displays and will be based on GSK data standards and statistical principles.

Unless otherwise specified, endpoints / variables defined in Section 7.3.1 will be summarized using descriptive statistics, graphically presented (where appropriate) and listed.

7.3.5.1. Statistical Methodology Specification

Endpoint / Variables

 Change from baseline in the respective iron parameter at each assessment visit
Model Specification

 Analyses will be repeated for each iron parameter (ferritin/TSAT/hepcidin/serum iron/TIBC) using MMRM as follows: $\text{Iron}_{ik} = \beta_0 + \beta_{\text{baseline}} * \text{Baseline}_i + \beta_j + \beta_k + \beta_{jk} + \beta_{\text{baseline}*k} * \text{Baseline}_i + \epsilon_{ik}$ 
Iron_{i, week}: change from baseline in iron measurement for subject i at visit k

β_0 : Intercept
 β_{baseline} : baseline effect of each iron parameter
 Baseline_i: the baseline value of each iron parameter for subject i
 β_j : treatment effect (j= daprodustat, epoetin beta pegol)
 β_k : visit effect (k = Week 4, Week 16, Week 28, Week 40, Week 52)
 β_{jk} : treatment-by-visit interaction
 $\beta_{\text{baseline}*k}$: baseline-by-visit interaction
 ϵ_{ik} : random error for subject i at visit k
 i: subject (i = PPD ..., N)
 N: number of subjects included in the analysis

- The model parameters will be estimated using Restricted Maximum Likelihood (method=REML) with the Newton-Raphson algorithm.
- The Kenward-Roger method for calculating the denominator degrees of freedom will be used.
- The variance-covariance structures for repeated measures within the individual subject will be unstructured (type=UN).
- LS mean change from baseline for treatment j at visit k will be calculated as follows for each iron parameter.

$$\mu_{jk} = \beta_0 + \beta_{\text{baseline}} * \mu_{\text{baseline}} + \beta_j + \beta_k + \beta_{jk} + \beta_{\text{baseline}*k} * \mu_{\text{baseline}}$$

μ_{jk} : LS mean change from baseline for treatment j at visit k
 μ_{baseline} : mean for the baseline value of each iron parameter

- The treatment difference at visit k for model based mean change from baseline will be calculated as follows for each iron parameter as adjusted treatment difference

$$\mu_{\text{daprodustat}*k} - \mu_{\text{epoetin beta pegol}*k} = \beta_{\text{daprodustat}} - \beta_{\text{epoetin beta pegol}} + \beta_{\text{daprodustat}*k} - \beta_{\text{epoetin beta pegol}*k}$$

- Note that log-transformed values will be used for TSAT and hepcidin in the MMRM analysis. The LS means for treatment j at visit k and the adjusted treatment difference at visit k will be exponentially back-transformed to the original scale and provided as follows:

Adjusted geometric mean percent change from baseline = $100 * (\exp(\mu_{jk}) - 1)$
 Adjusted ratio for percent change from baseline = $\exp(\mu_{\text{daprodustat}*k} - \mu_{\text{epoetin beta pegol}*k})$

Model Checking & Diagnostics

- In case there is a problem with convergence of the unstructured (type=UN) variance-covariance, the following strategy will be examined.
 1. Use Fisher's scoring algorithm for the estimation method.
 2. Set Heterogeneous Toeplitz (type=TOEPH) structure for variance-covariance structure.
 3. In the event of that this model still fails to converge, alternative correlation structures may be considered such as type=CSH or CS.

Model Results Presentation

- For ferritin, serum iron, and TIBC, the adjusted mean change from baseline will be presented with the associated 95% CIs by treatment at each assessment visit. The adjusted treatment

difference (daprodustat – epoetin beta pegol) for change from baseline will also be presented with the associated 95% CI at each assessment visit.

- For TSAT and hepcidin, the adjusted geometric mean percent change from baseline will be presented with the associated 95% CIs by treatment at each assessment visit. The adjusted ratio (daprodustat / epoetin beta pegol) for percent change from baseline will also be presented with the associated 95% CI at each assessment visit.

Subgroup Analyses

- For all of the respective iron parameter, the above analysis will be repeated by baseline iron use and prior ESA use subgroup (See Section 5.4.2) in the same manner.
- The subgroup analyses will be based on the ITT and Efficacy PD population.
- If there is a problem with convergence for a subgroup, the result of the subgroup will not be displayed.

7.4. Exploratory Efficacy Analyses

7.4.1. Endpoint / Variables

[Endpoint / Parameter/ Display Type]	Absolute					
	Stats Analysis		Summary		Individual	
	T	F	T	F	F	L
CKD progression (eGFR, serum creatinine, urine creatinine, urine albumin, urine albumin/creatinine ratio)						
Raw observed value at each assessment visit			Y	Y		Y
Change from baseline at each assessment visit			Y	Y		
Number (%) of subjects with eGFR decrease of 30% or more from baseline			Y			
Number (%) of subjects with serum creatinine increase of more than double from baseline			Y			
Other						
Scatter plot of change from baseline in Hgb at Week 4 vs. covariates of interest				Y		
Scatter plot of mean dose during Week 40 to 52 vs. covariates of interest				Y		

NOTES :

- T = Table, F = Figure, L = Listing, Y = Yes display generated.
- Stats Analysis = Represents TFL related to any formal statistical analyses (i.e. modelling) conducted.
- Summary = Represents TFL related to any summaries (i.e. descriptive statistics) of the observed raw data.
- Individual = Represents FL related to any displays of individual subject observed raw data.

7.4.2. Summary Measure

- **CKD progression (eGFR, serum creatinine, urine creatinine, urine albumin, urine albumin/creatinine ratio)**

Raw observed value at each assessment visits

The values will be summarized using mean, standard deviation, 95%CI, minimum, P25, median, P75, and maximum at each assessment visit by treatment group. Graphical summaries will be provided using mean and 95% CI over time.

Change from baseline at each assessment visit

The values will be summarized using mean, standard deviation, 95%CI, minimum, P25, median, P75, and maximum at each assessment visit by treatment group. Graphical summaries will be provided using mean and 95% CI over time.

Number (%) of subjects with eGFR decrease of 30% or more from baseline

The number and percentage of subjects with eGFR decrease of 30% or more from baseline will be summarized at each assessment visit by treatment group.

Number (%) of subjects with serum creatinine increase of more than double from baseline

The number and percentage of subjects with serum creatinine increase of more than double from baseline will be summarized at each assessment visit by treatment group.

- **Other**

Scatter plot of change from baseline in Hgb at Week 4 vs. covariates of interest

Scatter plot of change from baseline in Hgb at Week 4 versus following covariates of interest, body weight, baseline Hgb, prior ESA dose will be produced for the ITT and Efficacy PD populations. See Section 15.6.3 for the detailed derivations.

Scatter plot of mean dose during Week 40 to 52 vs. covariates of interest

Scatter plot of mean dose during Week 40 to 52 versus following covariates of interest, body weight, baseline Hgb, prior ESA dose will be produced for the ITT and Efficacy PD populations. See Section 15.6.3 for the detailed derivations.

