2.2. Study Objective(s) and Endpoint(s)

Objectives	Endpoints
Primary Objectives	Primary Endpoints

 To demonstrate non-inferiority of GSK1278863 to epoetin beta pegol based on hemoglobin (Hgb) in ND subjects 	
 Mean Hgb during the primary efficacy evaluation period (Weeks 40 to 52)
Principal Secondary Objectives	Principal Secondary Endpoints

 To demonstrate superiority of GSK1278863 to epoetin beta pegol in terms of achievement/maintenance of target Hgb in ND subjects 	
 Number (%) of subjects with mean Hgb in the target range (11.0-13.0 g/dL) during the primary efficacy evaluation period (Weeks 40 to 52)
Other Secondary Objectives	Other Secondary Endpoints

 To evaluate the appropriateness of the starting dose of GSK1278863 in ND subjects using epoetin beta pegol as control To evaluate the appropriateness of the starting dose of GSK1278863 in PD subjects 	
 Change in Hgb from baseline to Week 4 (Hgb increase rate) Number (%) of subjects by Hgb change category in Hgb from baseline to Week 4

 To evaluate dose adjustments of GSK1278863 in ND subjects using epoetin beta pegol as control To evaluate dose adjustments of GSK1278863 in PD subjects 	
 Distribution of the dose level Duration of treatment interruption due to Hgb >13 g/dL Frequency of dose adjustments

 To evaluate the overall Hgb control by GSK1278863 in ND subjects using epoetin beta pegol as control To evaluate the overall Hgb control by GSK1278863 in PD subjects 	
 Hgb at each assessment time point and change in Hgb from baseline to each assessment time point Number (%) of subjects with Hgb within the target range (11.0-13.0 g/dL) at each assessment time point Proportion (%) of time with Hgb within the target range (11.0-13.0 g/dL) in the primary efficacy evaluation period (Weeks 40 to 52) Time (number of days) to the lower Hgb target (11.0 g/dL) Number (%) of subjects who have an Hgb level of less than 7.5 g/dL Number (%) of subjects who have an Hgb increase of more than 2 g/dL over any 4 weeks before Week 52 Number (%) of subjects who achieve an Hgb level of more than 13.0 g/dL and number of episodes

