
 To compare the effect of GSK1278863 versus epoetin beta pegol on iron use in ND subjects To evaluate effect of GSK1278863 on iron use in PD subjects 	
 Dose of oral iron in the study period and the primary efficacy evaluation period (Weeks 40 to 52) Number (%) of subjects who use oral iron during the primary efficacy evaluation period (Weeks 40 to 52)

 To compare the effect of GSK1278863 versus epoetin beta pegol on iron metabolism in ND subjects To evaluate the effect of GSK1278863 on iron metabolism in PD subjects 	
 Change in ferritin from baseline Change in transferrin saturation (TSAT) from baseline Changes in hepcidin, serum iron, and total iron binding capacity (TIBC) from baseline

Objectives	Endpoints

 To evaluate the PK of GSK1278863 	
 AUC and Cmax of plasma GSK1278863
Exploratory Objectives	Exploratory Endpoints

 To compare the effect of GSK1278863 versus epoetin beta pegol on progression of CKD in ND subjects 	
 Estimated glomerular filtration rate (eGFR) and change from baseline Serum creatinine and change from baseline Urine creatinine and urine albumin, and changes from baseline Urine albumin/creatinine ratio and change from baseline
Patient Reported Outcome	Patient Reported Outcome Endpoints

 To compare the effect of GSK1278863 versus epoetin beta pegol on health-related QoL (HR-QoL) in ND subjects To evaluate the effect of GSK1278863 on HR-QoL in PD subjects 	
SF-36
 
 Changes in SF-36 HR-QoL scores (PCS, MCS, and 8 subscales) from baseline 
EuroQol Health Utility Index (EQ-5D-5L)
 
 Change in EQ-5D-5L score from baseline Change in EQ-5D-5L Visual Analog Scale (VAS) from baseline
Safety Objectives	Safety Endpoints

 To evaluate the safety and tolerability of GSK1278863 in ND and PD subjects 	
 Incidence and severity of AEs and SAEs, including AEs of special interest Reasons for discontinuation of study medication Laboratory tests, ECG, vital signs, and ophthalmology assessments

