5.5. Multiple Comparisons and Multiplicity

Adjustment for multiplicity will be applied to maintain an overall type I error rate of 2.5% (one-sided, change from define in the protocol, see Section 2.1). After a preliminary assessment, the primary endpoint will be evaluated to demonstrate the non-inferiority at a one-sided significance level of 2.5%. Only when the primary endpoint achieves non-inferiority, statistical testing will progress to the principal secondary endpoint with a focus on superiority. Since the process will follow step-down manner, a multiplicity adjustment for one-sided significance level of 2.5% will not be needed according to a closed test procedure.

Other secondary endpoints, which will be evaluated on a complementary or exploratory basis, will be compared at a two-sided significance level of 5% without multiplicity adjustment.

Since Cohort 2 is a single-arm cohort, no testing will be performed to evaluate the efficacy in PD subjects.

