7.4.5. Statistical Analyses / Methods

Details of the planned displays are provided in [Appendix 10: List of Data Displays](#) and will be based on GSK data standards and statistical principles.

Unless otherwise specified, endpoints / variables presented in Section [7.4.1](#) will be summarized using descriptive statistics, graphically presented (where appropriate) and listed.

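### CKD progression is set up as a comparison of the two arms but gets only arm-wise summaries, and the Week 4 Hgb difference that Section 5.5 implies is not specified for reporting

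*SAP*

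**What the plan says.** **CKD progression.** Section 2.2 gives the exploratory objective as "To compare the effect of GSK1278863 versus epoetin beta pegol on progression of CKD in ND subjects". Section 7.4.2 then plans descriptive statistics for the raw values and for change from baseline: "The values will be summarized using mean, standard deviation, 95%CI, minimum, P25, median, P75, and maximum at each assessment visit by treatment group". The event endpoints are treated alike, for example: "eGFR decrease of 30% or more from baseline will be summarized at each assessment visit by treatment group". Section 7.4.5 sets the default for the whole exploratory section: endpoints are "summarized using descriptive statistics, graphically presented (where appropriate) and listed". Tables 2.130 to 2.133 follow from this.

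**Week 4 Hgb change.** This is an other secondary endpoint under the objective "To evaluate the appropriateness of the starting dose of GSK1278863 in ND subjects using epoetin beta pegol as control". Section 5.5 says that other secondary endpoints "will be compared at a two-sided significance level of 5% without multiplicity adjustment". Section 7.3.2 plans arm-wise statistics by visit and arm-wise counts by change category (Tables 2.5, 2.7, 2.32 and 2.34).

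**The concern.** Two statements of intent are not carried through to the methods. For CKD, the report would contain no planned estimate of the quantity the objective names. For Week 4 Hgb, Section 5.5 announces a comparison that no method section specifies.

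The trial is open-label. If someone later wants either contrast, the model, covariates and handling of withdrawals would be chosen after the data are known. What is at stake is a pre-specified, baseline-adjusted exploratory interval, not any confirmatory conclusion.

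**Working it through.** No figure in the plan is in question, so the check sets sections side by side.

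**1. Is CKD treated like the other comparative objectives?** Section 2.2 has four objectives for non-dialysis subjects worded as comparisons of the two arms:

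| Objective | Between-arm estimate | Where |
|---|---|---|
| Iron use | Difference and 95% CI for change in oral iron dose, ITT | 7.3.2 |
| Iron metabolism | MMRM difference or ratio and 95% CI by visit | 7.3.2, 7.3.5.1 |
| HR-QoL | MMRM difference and 95% CI by visit | 9.2, 9.5.1 |
| CKD progression | None | 7.4.2, 7.4.5 |

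The empty statistical-analysis columns in Section 7.4.1 and the table titles do not settle this. Oral iron dose change and time in range have the same empty columns in Section 7.3.1 yet get a difference in Section 7.3.2, and the iron-parameter tables are titled as summaries although Section 7.3.5.1 models them. The evidence is the text of Sections 7.4.2 and 7.4.5, which specifies no contrast.

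**2. Does Section 5.5 reach each endpoint?** Its sentence covers other secondary endpoints. Week 4 Hgb change is one. CKD progression is listed as exploratory, so Section 5.5 does not govern it; there the mismatch is only with the wording of its own objective.

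**3. Is the Week 4 contrast already in the primary model?** Section 7.1.5.1 fits visits from Week 4 to Week 52 with treatment, visit, treatment-by-visit, baseline and baseline-by-visit terms, and defines an LS mean for each arm at each visit. At Week 4 the baseline terms cancel, leaving

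μ(dap, W4) − μ(epo, W4) = β(dap) − β(epo) + β(dap×W4) − β(epo×W4).

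The LS mean change is μ(j, W4) − μ(baseline), and μ(baseline) is common to both arms, so the difference in change equals the difference in Week 4 Hgb. The only treatment difference specified for output, however, is the average over Weeks 40, 44, 48 and 52. By-visit output is a curve for each arm. The contrast can be estimated but is not specified or reported.

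**4. Can the existing iron model carry the CKD measures?** Its visits (Weeks 4, 16, 28, 40, 52) are the post-baseline on-treatment clinical chemistry visits in Appendix 2, so eGFR and serum creatinine fit directly. Urinalysis on treatment is at Weeks 24 and 52 only.

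**5. Is the creatinine event ready for an odds ratio?** Section 15.6.6 defines change (%) = (creatinine − baseline) / baseline × 100 and flags change > 200. That means creatinine > baseline × (1 + 200/100) = 3 × baseline, which is more than tripling. More than doubling is change > 100, since 1 + 100/100 = 2. An odds ratio on the present flag would describe a different event from the one named.

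**The case against.** The case for leaving the plan alone has substance. The exploratory section is consistent within itself: intercurrent events are set aside, observed data are summarised, and the method is descriptive. Only the objective's wording points the other way. The Week 4 objective is to evaluate the starting dose with a control, not strictly to compare, and Section 2.3 gives different starting doses by cohort, ESA use and baseline Hgb, so one pooled difference averages over regimens. Baseline-adjusted model curves with 95% bands are planned for each arm, overall and by prior ESA use. Read literally, Section 5.5 would also require comparisons for dose, treatment interruption, Hgb below 7.5 g/dL and Hgb above 13.0 g/dL, which are likewise summarised only by arm.

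These points limit the finding but do not remove it. The last one shows that the sentence in Section 5.5 is too broad.

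Three stronger readings are not supported:

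- A reader might infer that a 5% testing commitment is broken for CKD. Section 5.5 does not cover exploratory endpoints.
- A reader might infer that no contrast can be obtained. The primary MMRM contains the Week 4 contrast, and a crude difference or odds ratio can be computed from the planned means, SDs and counts, though it would be unplanned and unadjusted.
- A reader might infer that the arms must be judged by whether their separate intervals overlap, with a loss of power. The SAP states no such rule, so error or power figures for it would not describe this plan.

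**Conclusion.** The point holds as a minor inconsistency between stated aims and specified methods, in two separate parts: CKD against its own objective, and Week 4 Hgb change against Section 5.5. The non-inferiority test and the principal secondary superiority test are unaffected. The conclusion rests on the SAP text alone. It assumes that the comparative wording of the CKD objective and the sentence in Section 5.5 are meant as written; if either was meant descriptively, the wording is what needs to change.

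**What to change.** 1. **Week 4 Hgb.** Report the daprodustat − epoetin beta pegol difference with 95% CI from the primary MMRM, overall and by prior ESA use because starting doses differ. The fit by prior ESA use is already planned in Section 7.1.5.1. It does not fully separate starting doses among Cohort 3 ESA non-users, and the text should say so.
2. **eGFR and serum creatinine.** Apply the Section 7.3.5.1 MMRM in ITT at Weeks 4, 16, 28, 40 and 52, and report the adjusted difference with 95% CI. Amend Section 7.4.4 to state the same hypothetical, missing-at-random strategy as Section 7.3.4; otherwise the model and the stated strategy would disagree.
3. **Urine parameters.** If they are modelled at Weeks 24 and 52, log-transform albumin and the albumin/creatinine ratio. Section 15.6.4 already allows this for other endpoints.
4. **Event counts.** Give an odds ratio with 95% CI for eGFR decrease of 30% or more, with covariates and visits stated, and leave it out when undefined, as Section 15.6.3 does for Hgb increase. Do the same for creatinine doubling only after Section 15.6.6 is corrected from change > 200% to change > 100%.
5. **Section 5.5.** Limit the sentence on comparison at 5% to secondary endpoints with a specified contrast, and call the rest descriptive.

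Label every added contrast exploratory and unadjusted for multiplicity. The cost is SAP wording and some table rows, with no new data. The downside is a few more unadjusted intervals to interpret.

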7.4.3. Population of Interest

The exploratory efficacy analyses will be based on the ITT population, unless otherwise specified.

7.4.4. Strategy for Intercurrent (Post-Randomization) Events

Any intercurrent events are taken to be irrelevant for exploratory endpoints. The exploratory endpoints will be summarized based on available and observed data.

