6. STUDY POPULATION ANALYSES

6.1. Overview of Planned Study Population Analyses

The study population analyses will be based on the specified population. For the populations including both ND and PD subjects (All Screening, Enrolled, Randomized, Safety), the summaries will be provided by dialysis (ND and PD separately) unless otherwise specified.

Study population analyses including analyses of subject's disposition, protocol deviations, population analysed, demographic and baseline characteristics, medical conditions and concomitant medications, and exposure and treatment compliance will be based on GSK Core Data Standards. Analysis of dialysis will also be included. Details of the planned displays are presented in [Appendix 10: List of Data Displays](#).

Endpoint / Parameter / Display Type	Population	Data Displays Generated		
		Table	Figure	Listing
Subject's Disposition				
Subject Status and Reason for Study Withdrawal	Randomized	Y		
Reasons for Study Withdrawal	Randomized			Y
Treatment Status and Reasons for Discontinuation of Study Treatment	Safety	Y		Y
Screening Status and Reasons for Screen Failure	All Screening	Y		Y
Subjects Enrolled by Country and Site ID	Enrolled	Y		
Planned and Actual Treatments	Safety			Y
Protocol Deviations				
Important Protocol Deviations	Randomized	Y		Y
Subjects with Inclusion/Exclusion Criteria Deviations	Randomized	Y		Y
Populations Analyzed				
Study Populations	Randomized	Y		
Exclusions from the Per Protocol Population	mITT	Y		Y
Subjects Excluded from Any Population	Randomized			Y
Composition of Randomized Population	Randomized	Y		
Demographic and Baseline Characteristics				
Demographic Characteristics	ITT/Safety/Efficacy ND/Efficacy PD	Y		Y
Demographic Characteristics by Prior ESA Use	ITT/Safety/Efficacy PD	Y		
Demographic Characteristics by Cohort	Efficacy ND	Y		
Other Baseline Characteristics ^[1]	Safety			Y
Prior ESA	ITT/Safety/Efficacy PD	Y		Y
Age Ranges	Enrolled	Y		
Race and Racial Combinations	Safety	Y		Y ^[1]
Family History for CV Risk Factors	Safety	Y		Y

Endpoint / Parameter / Display Type	Population	Data Displays Generated		
		Table	Figure	Listing
Substance Use (History of Tobacco Use, Alcohol Intake)	Safety	Y		Y
Dialysis				
Subjects with Dialysis Initiation during the Study Period	Safety			Y
Subjects with Peritoneal Dialysis at Baseline	Safety			Y
Subjects with Vascular Therapeutic Procedures during the Study Period	Safety			Y
Medical Conditions and Concomitant Medications				

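### Dialysis start is ignored in the CKD-progression event counts, so subjects who start dialysis can go uncounted at later visits and no table counts dialysis starts by arm

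*SAP*

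**What the plan says.** The exploratory objective in SAP section 2.2 is comparative: "To compare the effect of GSK1278863 versus epoetin beta pegol on progression of CKD in ND subjects".

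Section 7.4.4 sets one rule for everything that happens after randomization and one for the data used: "Any intercurrent events are taken to be irrelevant for exploratory endpoints. The exploratory endpoints will be summarized based on available and observed data". Dialysis start is not named, so it falls under the first of these.

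Section 7.4.2 plans two event counts, both by visit and by arm. One is headed "Number (%) of subjects with eGFR decrease of 30% or more from baseline"; a matching one covers a more than twofold rise in serum creatinine. Neither has a count of subjects with the event at any time. Section 15.6.6 derives both events from the change from baseline in that visit's laboratory value and does not mention dialysis.

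The SAP does expect dialysis to start in some subjects. Section 6.1 has a row for "Subjects with Dialysis Initiation during the Study Period", marked for a listing only, in the Safety population; it becomes Listing 52. Section 5.4.2 provides a subgroup for CKD stage 5.

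**The concern.** Starting dialysis is itself progression of CKD, and it also removes or alters the measurement used to detect progression. Treating it as irrelevant therefore suits this endpoint poorly. There are two routes by which a subject can drop out of the counts.

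- **No later value.** A subject who leaves the study contributes nothing at later visits. Section 15.2.1 schedules clinical chemistry after baseline only at Weeks 4, 16, 28, 40 and 52, early withdrawal and follow-up. Section 15.3.1 has no early-withdrawal analysis time point, so that sample does not clearly enter a by-visit count.
- **A value measured on dialysis.** A subject who stays may have a creatinine that no longer passes the threshold.

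At stake is whether Tables 2.132 and 2.133 describe progression in each arm, and whether the arms can be compared fairly if their dialysis rates differ.

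**Working it through.** The SAP states no event rate, dialysis rate or power for this endpoint, so there is no figure to reproduce. The steps below show what its rules do. All rates and creatinine values are assumptions.

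**1. Can a value on dialysis hide an event?** The equation in 15.6.6 makes eGFR proportional to creatinine to the power −1.094 (age held fixed). A 30% fall in eGFR needs creatinine to rise by a factor of 0.7^(−1/1.094) = 1.385. Assume a baseline creatinine of 4.0, rising to 8.5 before dialysis.

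| Creatinine | Change in creatinine | Change in eGFR |
|---|---|---|
| 8.5, before dialysis | +112.5% | −56.2% |
| 5.2, on dialysis | +30% | −25.0% |
| 7.0, on dialysis | +75% | −45.8% |

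At 5.2 the subject is an event under neither count. At 7.0 the subject still counts for eGFR but has not doubled creatinine. Hiding depends on the value reached. (Separately, 15.6.6 programs the creatinine event as a change above 200%, which is more than triple, so the pre-dialysis value here meets the endpoint as titled but not as programmed. That needs its own correction.)

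**2. Same true progression in both arms.** Let P be true progression including dialysis starters, and d the share who start dialysis, all of them progressors. The visit count shows (P − d)/(1 − d) if they are missing and P − d if they are measured but below threshold. With P = 30%:

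| d, arm A v arm B | Missing | False difference | Below threshold | False difference |
|---|---|---|---|---|
| 6% v 6% | 24/94 = 25.5% in both | 0 | 24% in both | 0 |
| 3% v 4% | 27/97 = 27.8% v 26/96 = 27.1% | about 0.8 points | 27% v 26% | 1 point |
| 6% v 12% | 24/94 = 25.5% v 18/88 = 20.5% | 5.1 points | 24% v 18% | 6 points |

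**3. Dialysis starts added to a common background.** Section 2.3 gives approximately 286 ND subjects randomized 1:1, so 286/2 = 143 per arm (illustrative; the ITT population excludes Cohort 1 ESA non-users). Assume 25% of those not on dialysis have the eGFR event, and 5% v 15% start dialysis (7 v 21 subjects).

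- Missing: 34/136 = 25.0% v 30/122 = 24.6%, difference −0.4 points. This is only rounding to whole subjects; the underlying rate is 25% in both.
- Below threshold: 34/143 = 23.8% v 30/143 = 21.0%, difference −2.8 points.
- Dialysis counted as an event: 41/143 = 28.7% v 51/143 = 35.7%, difference +7.0 points.

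Here the problem is mainly a real difference that does not show, rather than a false one that does.

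**4. Equal dialysis rates, understatement within each arm.** On the same basis, 5% in both arms gives 25.0% (missing) or 23.8% (below threshold) against 28.7%, short by 3.7 to 4.9 points. At 10% in both arms it is 24.8% or 22.4% against 32.2%, short by 7.4 to 9.8 points. The between-arm difference is 0 throughout.

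**The case against.** The stakes are low. CKD progression is exploratory, section 7.4.1 marks no formal analysis for it, and no treatment difference is planned. The SAP does not say whether dialysis start ends treatment or follow-up, so one of the two routes may never occur, and the view that dialysis lowers creatinine is general knowledge rather than something the SAP states. Table 3.105 also gives, by treatment group and including unscheduled assessments, the worst post-baseline eGFR against a criterion of a 40% or greater fall, which partly supplies an any-time count. Listings 52 and 63 allow cases to be linked by hand.

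All of this stands, and it limits the point without removing it. Table 3.105 uses a stricter threshold and the Safety population, and it does not count dialysis. Listings do not give a comparison by arm. Nor is a composite rule foreign to this plan: section 7.2.4 makes study withdrawal part of the response definition for the principal secondary endpoint.

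A reader might infer three stronger things that the document does not support.

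- **That dialysis starters are never counted as progressors.** Anyone who met a threshold at a visit before dialysis is counted at that visit, and some still meet the eGFR threshold on dialysis.
- **That the arm with more dialysis will look better.** That needs unequal dialysis rates, which nothing in the SAP suggests, and even then step 3 shows almost no displayed difference when values are missing.
- **That removing post-dialysis values cures the mean summaries.** It makes them interpretable, but they still describe only subjects not yet on dialysis.

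**Conclusion.** The point holds as a weakness in an exploratory comparison. Followed exactly, sections 7.4.4 and 15.6.6 let subjects who start dialysis go uncounted at later visits in Tables 2.132 and 2.133, and no output counts dialysis starts by arm.

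The size cannot be known from the SAP. With true progression equal in both arms, the assumed rates give a false difference from 0 to about 6 points, and exactly 0 when dialysis rates are equal. If dialysis starts add to a common background rate, a real 7.0-point difference is shown as roughly none or slightly reversed, under an assumed 5% v 15%. Within each arm the understatement is about 4 to 10 points at assumed dialysis rates of 5% to 10%. All these figures assume that every dialysis starter is a progressor and goes uncounted at the visit, so they are upper ends for the rates used.

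The primary and principal secondary conclusions are unaffected.

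**What to change.** - **7.4.4:** name dialysis start as an intercurrent event for the CKD endpoints and treat it as a component of the two progression events.
- **15.6.6:** count a subject as having each event from the recorded dialysis start date onward.
- **Tables 2.132 and 2.133:** add a row for an event at any time up to Week 52, and the number of dialysis starts by arm. Note that subjects who withdraw early for other reasons have incomplete follow-up, so the any-time row is not a complete count for them. The SAP does not show that dialysis starting after withdrawal is recorded, so the rule can use only recorded dates.
- **Tables 2.130 and 2.131 and their figures:** flag or exclude eGFR and creatinine after dialysis start, and state that these means describe only subjects not yet on dialysis.

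The cost is SAP wording and minor programming, since dialysis start is already collected. The small downside is that each event becomes a composite of a laboratory change and dialysis; showing dialysis starts separately keeps the two parts visible.
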